## **9. Research methods**

### **9.1. Study design**

This study is an international, prospective, open-label, multi-center, non-interventional study.

A prospective, non-interventional design was chosen, because the collection of data on real-life treatment can help to get a clearer picture of the clinical practice in HCC and on the influence this might have on patients' overall survival. Currently there is no homogeneous approach in the treatment of patients with HCC. In most countries TACE is a preferred treatment, but the range of patients it is used for, is wide. Though, in most countries it is one of the first therapeutic options for unresectable HCC, the number of TACEs as well as subsequent therapies are very flexible.

### 9.1.1. Primary endpoint(s)

The primary endpoint is overall survival (OS) from time of TACE non-eligibility.

OS is defined as the time interval from TACE non-eligibility to death due to any cause. Patients alive at the end of study will be censored at the last date known to be alive.

A patient is classified non-eligible for TACE, if at least one of the criteria in 9.3.8 except ‘advanced liver disease (Child-Pugh class B or C) is met.

Time of TACE non-eligibility is the first point in time in the study when TACE non-eligibility is met according to the documentation in the CRF. In case of a pre-existing TACE non-eligibility, time of TACE non-eligibility will be defined as the time of enrollment.

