### **9.3.8. Disease status summary**

The following criteria will be assessed at initial visit and every follow-up visit:

- lack of portal blood flow (because of portal vein thrombosis, portosystemic anastomoses or hepatofugal flow)
- Patients with lobar or segmental portal vein thrombosis.
- Patients with advanced liver disease (Child–Pugh class B or C)
- Clinical symptoms of end-stage cancer
- Extrahepatic spread (N1, M1)
- ECOG PS  $\geq 1$
- BCLC C or D
- Vascular invasion.
- Two or more consecutive incomplete necrosis (depositions (50%) of lipiodol) are seen by response evaluation CT within the treated tumors at the 4 weeks after adequately performed TACE. (excluded from initial visit)
- Two or more consecutive appearances of a new lesion (recurrence) are seen in the liver by response evaluation CT at the 4 weeks after adequately performed TACE. (excluded from initial visit)
- TACE failure by investigator’s assessment (excluded from initial visit)
- Clinical encephalopathy
- Refractory ascites
- Hepatorenal syndrome
- Extensive tumor with massive replacement of both entire lobes
- Technical contraindications to hepatic intra-arterial treatment
- Renal insufficiency (creatinine  $\geq 2$  mg/dL or CrCl  $< 30$  mL/min)
- Other (to be specified)

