#### **9.7.4. Analysis of primary outcome(s)**

The primary efficacy endpoint is Overall Survival (OS). It is defined in this study as the time (days) from time of TACE non-eligibility to death due to any cause. Patients lost to follow-up or alive at the end of the study will be censored at the last date known to be alive.

For statistical evaluation, two patient cohorts of special interest will be compared regarding the primary endpoint. These two cohorts are defined as:

- Cohort 1: Patients with early start of Sorafenib treatment. This cohort comprises all patients where the physician decides at the time of TACE non-eligibility to choose Sorafenib as the next treatment option (regardless of whether TACE treatment is continued or not).
- Cohort 2: Patients without early start of Sorafenib treatment. This cohort comprises all patients where the physician decides at the time of TACE non-eligibility not to choose Sorafenib as the next treatment option.

This cohort also includes patients with TACE non-eligibility for whom the decision to treat with Sorafenib is made at a later points in time, patients who are never treated with Sorafenib as well as patients for whom another systemic cancer treatment has been chosen by the physician either at time of TACE non-eligibility or at a later point in time.

According to the definition of the two cohorts, patients where no TACE non-eligibility occurred during the study do not qualify for this analysis. In addition, patients treated with Sorafenib or any other systemic anti-cancer treatment prior to time of TACE non-eligibility are excluded from this analysis. These groups will be described separately.

As part of the descriptive analysis, Kaplan-Meier (KM) estimates for OS will be displayed for the two patient cohorts of special interest.

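### Two judgement items can start the primary survival clock at the visit where the same physician's choice fixes the cohort, so time zero can depend on the treatment chosen

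*Protocol*

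**What the plan says.** Section 9.1.1 sets the clock by a one-item rule: "A patient is classified non-eligible for TACE, if at least one of the criteria in 9.3.8" is met, apart from Child-Pugh class B or C. The date follows from the record: "Time of TACE non-eligibility is the first point in time in the study when TACE non-eligibility is met according to the documentation in the CRF". A separate rule covers patients who already qualify at entry: "In case of a pre-existing TACE non-eligibility, time of TACE non-eligibility will be defined as the time of enrollment".

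The list in section 9.3.8 includes "TACE failure by investigator’s assessment (excluded from initial visit" and "Other (to be specified". Neither is excepted in 9.1.1 and neither has an objective definition. The first counts at follow-up visits only; the second can count at any visit.

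Section 9.7.4 ties the cohort to the same time point. For cohort 1: "This cohort comprises all patients where the physician decides at the time of TACE non-eligibility to choose Sorafenib as the next treatment option". For cohort 2: "This cohort comprises all patients where the physician decides at the time of TACE non-eligibility not to choose Sorafenib as the next treatment option". The section also removes patients who never become non-eligible and patients given sorafenib or another systemic therapy before non-eligibility.

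Table 2 in section 9.3 requires the disease status summary and the decision on further treatment at each follow-up visit. Section 9.1 describes the study as open-label, and section 9.3.11 says that reasons for treatment choice are not captured in detail.

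**The concern.** In a cohort comparison, the start of follow-up should not depend on the exposure. Here one unblinded physician can record the item that starts the clock and the decision that assigns the cohort, at one visit.

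The exclusions in 9.7.4 make this potentially asymmetric. For a patient with no other counted criterion, a judgement item is the only route into cohort 1, because sorafenib started before non-eligibility leads to exclusion. A similar patient who gets another TACE with nothing ticked is not yet under observation for this endpoint. That patient enters later on another criterion, or never.

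The judgement item can also come earlier than its imaging counterparts. The two imaging-based failure items in 9.3.8 need at least two consecutive findings after TACE, whereas the investigator's assessment needs none.

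If cohort 1 is more often clocked early in this way, and patients rarely die in the added interval, that interval counts as survival gained.

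**Working it through.** **Planned figure.** Inputs from section 9.5: medians 9 and 12 months, exponential survival, 250 per cohort, 18 months of enrollment, 36 months in total, one-sided alpha 2.5%.

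- Event probability with λ = ln 2 / median: 1 − [exp(−18λ) − exp(−36λ)] / (18λ). This gives 0.780 (median 12) and 0.865 (median 9).
- Events: 250 × (0.780 + 0.865) = 411.
- Power (Schoenfeld): Φ(√(411/4) × |ln 0.75| − 1.96) = Φ(0.96) = 83%, as stated.

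**Lead-time model.** No treatment effect; both cohorts have a median of 9 months after the late trigger, with the same accrual and censoring as above. A share f of cohort 1 starts the clock L months early, and the hazard in that interval is r times the later hazard. L is one visit interval, which section 9.2.5 assumes to be 6 to 12 weeks: 6 × 7 / 30.44 = 1.38 months and 12 × 7 / 30.44 = 2.76 months. The protocol gives neither f nor r, so both are assumptions.

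Two cases follow without simulation:

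- r = 1: a constant hazard has no memory, so an earlier start leaves the hazard ratio at 1.00 for any f and L.
- f = 100%: the cohort 1 median becomes 9 + (1 − r)L. With r = 0 this is 10.4 to 11.8 months, an apparent gain of 1.38/3 = 46% to 2.76/3 = 92% of the planned 3 months.

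Simulated apparent hazard ratio (300,000 per cohort), 6 weeks / 12 weeks:

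| Share of cohort 1 affected | r = 1 | r = 0.5 | r = 0 (no deaths in the lead) |
|---|---|---|---|
| 25% | 1.00 / 1.01 | 0.99 / 0.97 | 0.97 / 0.94 |
| 50% | 0.99 / 1.00 | 0.97 / 0.95 | 0.95 / 0.88 |
| 100% | 1.00 / 1.00 | 0.94 / 0.89 | 0.89 / 0.79 |

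Departures from 1.00 in the r = 1 column are simulation error.

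Chance of one-sided p < 0.025 with no effect (250 per cohort, 2,000 runs), for 25%, 50% and 100% affected:

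- r = 0: 6%, 9% and 23% at 6 weeks; 10%, 24% and 69% at 12 weeks.
- r = 1: 2% to 3% throughout.

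**The case against.** The strongest reply is that the protocol establishes neither direction nor size, and most of that reply stands.

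- A judgement item sets time zero only if no other counted criterion was recorded earlier or at the same visit. The others are broad (ECOG PS of 1 or more, BCLC C or D, vascular invasion, extrahepatic spread). The share of patients triggered by judgement alone is not given.
- The status summary is completed whatever treatment follows, so a physician who repeats TACE can also record TACE failure. The cohorts are not a clean contrast of sorafenib against repeat TACE either: cohort 1 allows continued TACE, and cohort 2 includes other systemic therapy and later sorafenib.
- There is an opposing force. Patients enroll when TACE has been decided, and BCLC stage B or higher is allowed. Those already non-eligible are clocked from enrollment, and many may fall in cohort 2 with an early clock of their own.
- Section 9.7.8 lists covariates at non-eligibility (BCLC stage, tumor size, vascular invasion, extrahepatic spread) and response to the last TACE. These may absorb part of the difference. Section 9.1.2 adds survival from initial TACE, whose clock does not use the judgement items, although cohort membership still does.

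What does not stand is that this is only detail for the SAP. Time zero and the cohorts are rules fixed in the protocol. Covariates measured at a time zero that depends on treatment cannot restore patients who never entered the analysis. Section 9.8.4 admits channeling and confounding by indication but does not mention time zero.

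**Conclusion.** The concern holds as a possible bias: as written, time zero and cohort entry can depend on the treatment chosen, and this can give cohort 1 a lead. The net direction is undetermined.

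With no true effect and a lead of one visit interval, the apparent hazard ratio lies between 1.00 (equal hazard) and 0.94 with a quarter of cohort 1 affected. It reaches 0.79 only in the extreme corner of everyone affected, a 12-week lead and no deaths in it. These results rest on assumed values for share, lead and lead-interval hazard. A lower hazard in the lead is plausible for patients with no objective criterion, but the protocol does not state it.

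A reader might infer that the rule does favor sorafenib, or that lead time alone could produce the whole planned gain from 9 to 12 months. The documents support neither. The second would need every cohort 1 patient to enter 3 months early, which is longer than the assumed visit interval, with no deaths in that time. The plan's 83% power is unaffected.

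This should be addressed, because the planned effect is only a hazard ratio of 0.75 and even a partial bias would affect its reading.

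**What to change.** In section 9.7.4, pre-specify a sensitivity analysis of the primary endpoint:

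- Time zero is the first objectively documented counted criterion of 9.3.8, leaving out the investigator's assessment of TACE failure and the open category. State how other judgement items are classed, such as clinical symptoms of end-stage cancer and technical contraindications.
- The cohort is assigned from the treatment decision at that visit.
- Patients already on systemic therapy by then are excluded, as 9.7.4 already requires.

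Tabulate the triggering criterion by cohort and report both hazard ratios side by side. Read any difference as possible time-zero bias or as the effect of a changed population. A formal rule that both analyses must agree would not suit a study that section 4 describes as explorative and descriptive.

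The cost is one added analysis and one table, from items already on the CRF. The analysis will have fewer patients and wider intervals, and it loses cohort 1 patients who started sorafenib on a judgement trigger alone. By section 9.7.1 neither interim analysis includes the formal cohort comparison and the SAP is finalized before database lock, so the addition can still be made without sight of that comparison. The SAP was not available for this review; if it already holds such an analysis, a cross-reference in 9.7.4 is enough.

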### 9.1.2. Secondary endpoint(s)

The secondary endpoints for all patients and the two cohorts of special interest are:

- Overall Survival (OS) from initial TACE is defined as the time interval from the day of the first TACE to death due to any cause. Patients alive at the end of the study will be censored at the last date known to be alive.
- Progression-free survival (PFS) from initial TACE is defined as the time interval measured from the day of the first TACE to documented (radiological or clinical) progression or death, whichever comes first.
- Time to progression (TTP) from initial TACE is defined as the time interval from the day of first TACE to the date of documented progression. Patients without tumor progression at the end of the study will be censored at their last date of tumor evaluation.
- Tumor response to TACE by mRECIST will be evaluated according to the categories “Complete Response”, “Partial Response”, “Stable Disease”, and “Not evaluable” by mRECIST for each TACE.
- Duration of TACE treatment is defined as the time interval from of the day of first TACE to the date of permanent discontinuation of TACE (when an investigator decides TACE is no longer applicable regardless of the reason for discontinuation including death).
- TACE unsuitability will be determined according to the selected guidelines including AASLD, APASL, JSH, EASL-EORTC guidelines ...etc.
- Time to TACE non-eligibility will be determined according to the selected guidelines including AASLD, APASL, JSH, EASL-EORTC guidelines ...etc.
- Deteriorations of liver dysfunction will be evaluated throughout the study. Deteriorations of liver dysfunction are defined as below
  - Deterioration of Child-Pugh score (A5, A6, B7, B8, B9)
  - Liver dysfunction reported as AE or deterioration of AST, ALT or Bilirubin (from Grade1 to Grade 2-5, from Grade 2 to 3-5, Grade 3 to Grade 4 or 5.)
  - Any liver related adverse events or deterioration of liver related events according to CTCAE Version 4.03
  - Change of liver related lab data (AST, ALT, Bilirubin, Alb, INR)

Specific secondary endpoints for patients treated with sorafenib are:

- Overall survival (OS) from initiation of sorafenib is defined as the time interval measured from start date of sorafenib treatment to death due to any cause. Patients alive at the end of study will be censored at the last date known to be alive.
- Progression-free survival (PFS) from initiation of sorafenib is defined as the time interval measured from the start date of sorafenib treatment to documented (radiological or clinical) progression or death, whichever comes first.
- Time to progression (TTP) from initiation of sorafenib is defined as the time interval from start date of sorafenib treatment to the date of documented progression. Patients without tumor progression at the end of the study will be censored at their last date of tumor evaluation.
- Duration of sorafenib treatment is defined as the time interval from start date of sorafenib treatment to the date of permanent discontinuation of sorafenib treatment (regardless of the reason for discontinuation including death).
- The tumor status at different visits response according to mRECIST will be evaluated according to the categories “Complete Response”, “Partial Response”, “Stable Disease”, “Clinical Progression”, “Radiological Progression”, and “Not evaluable at this visit”. The best overall response will be analyzed providing absolute and relative frequencies of the tumor status categories.
- Incidence of Treatment-emergent Adverse Events (TEAEs) – patients will be monitored for TEAEs using the NCI-CTCAE Version 4.03. Details on the collection, management and reporting of TEAEs can be found in section 11.

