### **9.2.2. Inclusion criteria**

- Patients with histologically/cytologically documented or radiographically diagnosed HCC. Radiographic diagnosis needs typical findings of HCC by radiographic method i.e. on multi-dimensional dynamic CT, CT hepatic arteriography (CTHA)/CT arterial portography (CTAP) or MRI.
- Patients with BCLC stage B or higher.
- Patients in whom a decision to treat with TACE has been made at time of study enrollment. Patients that have received one TACE in the past also can be enrolled, if the TACE was done at the same site and all required data about such previous TACEs are available. TACE

includes both conventional TACE with lipiodiol (or similar agents) and chemotherapeutic agent(s) and TACE with DC Beads® excluding TAE without chemotherapeutic agent.

- Patients with unresectable HCC (incurable with curative treatments including resection or ablation or not eligible for resection or local ablation)
- Patients must have signed an informed consent form
- Patients must have a life expectancy of at least 8 weeks

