### **9.2.5. Visits**

The start of the study is the date from which information on the first study subject can be first recorded in the study dataset. The end of the study is date after which the last enrolled subject will have been in the study for 18 months, or is lost to follow-up or has died.

The investigator documents an initial, follow-up visits and a final visit for each patient in the case report form (CRF). After the initial visit at least one follow-up visit should be documented. A certain number or frequency of visits is not requested by this protocol. Documentation follows the actual clinical practice. A visit is defined as any status assessment or new treatment decision the treating physician takes with the presence of the patient. The time interval between two documented status assessments is assumed to be 6 - 12 weeks, although this will be at the treating physician's discretion.

In the case that the first TACE is documented retrospectively under the pre-requisites detailed in section 9.2.2. the baseline data asked in the initial visit also has to be documented retrospectively.

The final data collection (last visit) is at patient's death or at end of study (whatever is earlier). If the documentation is stopped prematurely, the reasons for the end of observation have to be given. If a patient will join an interventional clinical study during the course of observation, at least the information on survival will still be collected up to the end of this study.

The observation period for each patient is estimated to be about 18 months and covers the period from first TACE to death. If a patient will still be alive at time of study closure, this will be documented in the final visit.

The CRF is available upon request. The respective document is listed in Annex 1.

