### **9.3.9. Tumor assessment**

Patients will be assessed for response to TACE and tumor assessment preferably by mRECIST. In case that an assessment by mRECIST is not possible, because this is not routinely done at the site of the treating physician, also other evaluation criteria can be used. In any case the criteria used have to be documented along with the tumor evaluation and the physician should use the same criteria throughout all tumor evaluations of one patient.

TACE response to most recent TACE will be assessed within 12 weeks after TACE and recorded for each TACE.

Response evaluation will also be done compared to initial TACE. For patients treated with sorafenib, response evaluation compared to initiation of sorafenib will be added.

Tumor assessment will be made at physicians' discretion using CT scan or MRI or equivalent imaging exam, starting from initial TACE.

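### OS from initial TACE counts guaranteed survival for patients enrolled after their first TACE; the protocol needs a delayed-entry rule for OS, while the direction for PFS and TTP is open

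*Protocol*

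**What the plan says.** Protocol Section 9.1.2 starts three secondary endpoints at the first TACE:

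- OS: "Overall Survival (OS) from initial TACE is defined as the time interval from the day of the first TACE to death due to any cause". The censoring date for survivors is when they were last known to be living.
- PFS: "time interval measured from the day of the first TACE to documented (radiological or clinical) progression or death, whichever comes first".
- TTP: "time interval from the day of first TACE to the date of documented progression".

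Enrolment may come later than that origin. Section 9.2.2 states: "Patients that have received one TACE in the past also can be enrolled, if the TACE was done at the same site", provided the required data on it are available. No maximum interval is given. For these patients Section 9.2.5 requires that "the baseline data asked in the initial visit also has to be documented retrospectively", and it says that observation "covers the period from first TACE to death". Section 10.4 requires written consent before any data are documented. Section 9.3.9 has tumor assessment "starting from initial TACE". Section 9.7.5 takes everyone with at least one TACE into the Overall cohort and does not separate late entrants.

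The primary endpoint is handled differently. In Section 9.1.1 the clock is set to enrolment when TACE non-eligibility already existed.

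**The concern.** A patient whose first TACE preceded consent must have survived to consent in order to be in the dataset. Measured from the first TACE, that interval cannot contain a death, and patients who did die in it are never seen. This is left truncation. A Kaplan-Meier estimate that places such patients at risk from day 0 has too many people in its early risk sets and is biased upward. Section 9.1.2 fixes the origin and the censoring rule but has no rule for entry into the risk set.

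OS from initial TACE in all patients is a stated secondary objective (Section 8.2). Section 9.1.2 lists it for all patients and for both cohorts of special interest, and Section 9.7.7 summarizes OS by TACE procedure and region. If the share of late entrants differs between regions, part of any regional survival difference would be an artefact of enrolment.

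**Working it through.** **The plan's own figure.** The protocol states no expected value for any endpoint from initial TACE. Its only power figure (Section 9.5) concerns OS from TACE non-eligibility. With exponential survival, accrual a = 18, total T = 36 and minimum follow-up f = 18 months, the probability of death is 1 − [exp(−λf) − exp(−λT)]/(λa), where λ = ln 2/median.

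- Median 12: 0.780 × 250 = 195.0 deaths. Median 9: 0.865 × 250 = 216.2 deaths. Total 411.2.
- Power = Φ(√411.2/2 × |ln 0.75| − 1.96) = Φ(2.917 − 1.96) = 0.831, against 83% stated.

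This reproduces, and nothing below enters into it.

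**Size of the OS bias.** The inputs are all assumptions, because the protocol gives none of them: true median m, share q of patients enrolled late, and gap g from first TACE to enrolment. With exponential survival, the apparent survival curve for t > g is

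(1 − q)·exp(−λt) + q·exp(−λ(t − g)) = exp(−λt)·[(1 − q) + q·exp(λg)].

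Setting this to 0.5 gives

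apparent median − m = ln[(1 − q) + q·exp(λg)]/λ, which is roughly q × g.

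Example with m = 18, q = 30%, g = 3: λ = 0.0385 and exp(λg) = 1.1225. The bracket is 0.7 + 0.3 × 1.1225 = 1.0367, and ln(1.0367)/0.0385 = 0.94 months.

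Overstatement of the median, in months:

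| m | q | g = 1 | g = 3 | g = 6 |
|---|---|---|---|---|
| 12 | 10% | 0.10 | 0.32 | 0.70 |
| 12 | 30% | 0.31 | 0.96 | 2.03 |
| 12 | 50% | 0.51 | 1.56 | 3.26 |
| 18 | 10% | 0.10 | 0.32 | 0.67 |
| 18 | 30% | 0.30 | 0.94 | 1.95 |
| 18 | 50% | 0.50 | 1.54 | 3.17 |
| 30 | 10% | 0.10 | 0.31 | 0.64 |
| 30 | 50% | 0.50 | 1.53 | 3.10 |

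**Check by simulation** (200,000 patients per scenario, 18 to 36 months of follow-up after entry), ordinary against delayed-entry Kaplan-Meier median:

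- m = 18, q = 10%, g = 3: 18.36 against 18.04
- m = 18, q = 30%, g = 3: 18.93 against 17.97
- m = 12, q = 50%, g = 6: 15.31 against 12.03

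Delayed entry recovers the true median. The simulation assumes that entry is unrelated to prognosis.

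**Regions.** Take two regions with the same true median of 18 months and a 3-month gap, one with 10% and one with 50% late entrants. Their apparent medians would differ by 1.54 − 0.32 = 1.22 months.

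**TTP.** Assume a true median of 6 months, q = 30% and g = 3. In the whole population, 1 − exp(−λg) = 29% progress within 3 months. The ordinary median depends on how many late entrants had already progressed, with that progression recorded:

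- none: 7.0 months
- 30%: 6.0 months
- 50%: 5.2 months

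The bias can be upward, absent or downward.

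**The case against.** The strongest reply is that Section 9.1.2 only defines an origin and an event, both of which stay right under delayed entry. Section 9.7.1 leaves statistical details to the SAP, and Kaplan-Meier is specified only for the primary OS (Section 9.7.4). Only the protocol was available here, so the SAP may already contain the rule. That limits certainty but does not remove the point. The endpoint and entry rules, followed as written, give a biased OS. The protocol resets the clock to enrolment for pre-existing non-eligibility in the primary endpoint and has no counterpart here.

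It is also fair that the impact is limited. The endpoint is secondary, the abstract calls the analyses explorative and descriptive, and Section 9.8.4 concedes selection bias in general terms. Only one earlier TACE is allowed, at the same site and with complete data, and enrolment should be consecutive (Section 9.2.4). All of this may keep the share and the gap small.

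Two stronger readings do not hold:

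- A reader might infer that PFS and TTP are overstated in the same way. Only death is barred before enrolment. Sections 9.2.2 and 9.2.3 do not require freedom from progression, and tumor assessment runs from the initial TACE.
- A reader might infer that early TACE failures are excluded, because a decision for TACE is needed at enrolment. Section 9.1.1 expressly provides for pre-existing non-eligibility and Section 9.2.2 admits BCLC stage B or higher, so this is not established.

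**Conclusion.** The point holds for OS from initial TACE. Unless risk sets start at enrolment, the estimate is biased upward by about the late share times the mean gap. Under assumed shares of 10% to 50%, gaps of 1 to 6 months and exponential survival with medians of 12 to 30 months, the median is overstated by about 0.1 to 3.3 months. The actual amount cannot be stated, because the protocol gives neither share nor gap.

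For PFS and TTP from initial TACE the direction is undetermined. Distortion of regional comparisons is possible, but nothing in the protocol shows that the late share varies by region. The primary endpoint and its 83% power are unaffected. This is a cheap improvement, not a flaw in the main comparison.

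**What to change.** - In Section 9.1.2, state that for OS from initial TACE the clock starts at the first TACE but a patient joins the risk set only at enrolment when enrolment came later. Apply the same rule to the OS summaries by region and TACE procedure in Section 9.7.7.
- Add a sensitivity analysis of OS, PFS and TTP from initial TACE restricted to patients whose first TACE was on or after enrolment.
- Do not make delayed entry the sole analysis of PFS and TTP, because it would discard recorded progressions that precede enrolment.
- If the SAP already has such a rule, one aligning sentence in the protocol is enough.

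The cost is a sentence or two and an entry-time option in the survival procedure. TACE dates are collected (Section 9.3.10), and Section 9.1.1 already uses the time of enrolment. Intervals early in the OS curve become somewhat wider. Delayed entry does not remove bias if entry itself depends on prognosis; the restricted analysis is a partial check on that.
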